#### **D. Research Design and Methods:-**

**Overview:** This is a 5-year study designed to support a RCT that compares a new treatment, GCBT, with *SGP*. Two aims are involved in this project. The **first specific aim** is to examine if GCBT produces significant reductions in PTSD relative to the *SGP* condition and

to determine if these changes are durable across a 12 month follow-up interval. The **second specific aim** is to examine the generalizing effects of both GCBT and *SGP* on co-morbid conditions (depression, generalized anxiety, and alcohol abuse), distress, and impairment. Staff training, data-base construction, and preparation of materials will facilitate project integrity during the initial months of the proposed project. The RCT will involve 60 months, in which 196 male veterans with combat-related PTSD will be randomly assigned to GCBT ( $n= 98$ ) or *SGP* ( $n=98$ ) to determine efficacy in a naturalistic care environment. Outcome data will be collected pre-treatment, mid-treatment, post-treatment, and , 3-, 6-, and 12-month follow-up (see **Table 3**).

#### **D. 1. Study Participants:**

**Study Criteria:** Participants will include 196 male veterans. The participant must: (1) currently meet DSM-IV (American Psychiatric Association, 2000) criteria for chronic, PTSD (symptoms lasting 3 months or more) and (2) be free of psychosis and impaired cognitive function caused by traumatic brain injury or dementia. Exclusion criteria include: (1) a current diagnosis of substance dependence or unstable bipolar disorder, (2) currently involved in active treatment (individual or group) for PTSD, (3) substantial cognitive impairment that would negatively impact ability to engage in group PTSD treatment. The Clinician Administered PTSD - 5 Scale (CAPS-5;) will be used to establish DSM-IV diagnosis of current PTSD. The Structured Clinical Interview for DSM-IV (SCID, Spitzer, Williams, Gibbons, & First, 1994) will be used to evaluate psychosis, substance dependence, and bipolar disorder, as well as to assess for additional co-morbid anxiety and depressive disorders. The Wide Range Achievement Test (WRAT) reading subscale will be used to assess reading level. The Montreal Cognitive Assessment (MoCA; Nasreddine et al., 2005) will be used to assess cognitive function. The MoCA is a relatively new instrument and was selected because it appears to be considerably more sensitive and specific with mild cognitive impairment. A cut-off score of 20 in combination with clinical judgment will be used to determine cognitive impairment (and exclusion from participation; Nasreddine et al., 2005). Information about current participation in psychological therapy will be obtained during the initial screening and from chart review.

**Medication:** Participants will be asked to maintain stable levels of psychotropic and pain-relieving medication throughout their participation. Although one could argue that participants should be removed from psychotropic medication, this choice (although methodologically sound) would pose considerable risks from a human subjects' perspective. Some of the men who will participate in this trial have required psychotropic medication for many years, given chronicity of their conditions. Medication discontinuation could increase distress in these men to an unacceptably high level. From a scientific standpoint, maintaining a stable medication regimen during treatment mirrors typical clinical practice and ensures that the results of this trial can be generalized to practice. As such, we will address this issue by asking participants to maintain a stable dosage of medication throughout their participation and will secure permission to inform the prescribing physicians about our treatment program and this request.

Participants will be required to meet psychotropic medication stabilization criteria for the periods preceding and overlapping with the diagnostic assessment and treatment. Patients using anxiolytics and beta-blockers will be required to maintain the same dosage for at least 1 month. Patients on antidepressants (tricyclics, SSRIs, MAO inhibitors) need to have maintained a stable dosage for at least 3 months. If a patient is in the process of stopping his medication when he requests to be in the study, the medication wash-out period (i.e., period since medication discontinuation) will be 1 month for all medications. Those individuals who are using prescription medication will be asked to maintain written records of their use, including any changes that occur. In the event that we have a substantial number of individuals who change their medication during the course of treatment (despite the request not to), we will examine potential differences in treatment outcome between individuals whose medications remain stable versus changed using descriptive statistics.

**Diagnostic Procedures, including Training and determination of reliability:** The CAPS-5 and the SCID will be used to establish current PTSD diagnosis, to characterize current co-morbid psychiatric problems, and to rule out current psychosis, unstable bipolar disorder and substance dependence. Doctoral-level staff will be trained in the administration of these instruments, following the procedures outlined by DiNardo et al. (1993). These procedures include successfully matching criterion diagnoses for 3 of 5 training tapes, as well as demonstrating competency in administering interviews. [name] will oversee assessor training at the two sites. Additionally, all assessors will rate standardized diagnostic interviews (once every 3 months) to prevent rater drift. Assessors will be certified to administer the CAPS and SCID when they match criterion diagnoses and competently administer these instruments during a supervised interview. Throughout the trial, all interviews will be recorded and 25% will be selected at random for review by an Independent Reliability Evaluator. This individual will watch the recorded interview and provide a diagnostic profile. S/he will remain unaware as to participants' group assignment or the assessment time-point, in order to permit objective assessment of diagnostic reliability. Discrepancies between the Independent Reliability Evaluator's and the independent assessor's ratings will be resolved through consultation with the PI.

Assessors will be blinded to treatment condition assignment. We will protect assessors from knowing the treatment condition assignment using several methods. First, we are hiring assessors for this trial on a fee for service basis. Thus, they will not be staff specifically hired for this project and will therefore have limited information regarding the project and they will not have access to the study research database. In addition, assessors might know who the therapists are who are working on the proposed clinical trial, but they will not be told who the therapists are in each of the two treatment conditions. This will protect against the blind being broken if a participant mentioned the name of his therapist during the assessment. Assessors will be informed of the name of the veteran who they will be assessing but they will not be provided with any additional information, and the assessors will be instructed not to ask participant about their treatment experience in the study. Also, participants will be informed not to disclose any information about their treatment to the assessor. As all assessment sessions will be recorded we will conduct a random review of a portion of the assessment sessions to make sure that no information is disclosed during the assessment that would break the blind of

the assessor. If assessors believe information was obtained that breaks the blind to the treatment assignment of a participant, we will request that the assessor report this information to the project coordinator. We will track all such instances. One additional method by which we will ensure assessors are blinded to treatment condition is that assessors will all be supervised by [name]. They will not receive any supervision from the therapy supervisors in the study.

**CAPS:** The CAPS is the gold standard interview for evaluating PTSD (Weathers et al., 2001) and includes ratings for each PTSD symptom, rated on 0-4 behaviorally-anchored scales. As APA has approved diagnostic criteria changes for upcoming DSM-5, we will use the CAPS-5 version for this study. Both PTSD diagnosis and PTSD symptom severity will be included as treatment outcome variables in this study.

**SCID:** The SCID includes questions assessing each of the DSM-IV adult disorders (Spitzer, et al., 1994). Each disorder is coded as present, not present, or probable, based on structured questions that map onto the DSM-IV criteria. Additionally, each diagnostic category will be scaled with a Clinical Severity Rating (CSR) of 0 to 8, where a rating of 4 or higher represents clinical levels of interference or distress (see Appendix for CSR scale). Individuals receiving a CSR of 4 or higher for substance dependence disorders or bipolar disorder or reporting any psychotic symptoms will be excluded.

In the event that the DSM-V is released prior to the start of the proposed project and CAPS and SCID are revised accordingly, we will use the versions of the instruments that correspond with the DSM-V.

**Availability of Participants and Recruitment Process:** Recognizing the multiple challenges of recruiting for a group clinical trial for PTSD, we have included two recruitment sites in the proposed project. Although the majority of recruitment will come from the PTSD clinics at the VA Boston (Jamaica Plain campus) and VA Providence sites, we will conduct additional recruitment efforts. These additional efforts will include community-based outpatient clinics, additional mental health clinics within the two VA sites (e.g., Brockton campus PTSD clinic at VA Boston, General Mental Health Clinic at JP and Brockton), and primary care clinics.

One challenge in recruiting from clinics is that clinicians may be aware of suitable participants. However, due to confidentiality, the clinicians cannot provide any information about potential veteran participants to the project staff. We are aware that other investigators at VA Boston Healthcare System have found that including the 10-5345 form has permitted research staff to more effectively reach veteran participants who express interest in the program but who may have not actively called study staff on their own, due to PTSD symptomatic avoidance reasons. Therefore, we will include the 10-5345 form in this study in order to more effectively reach potential participants. This form will be provided to veterans who express interest in the study during outreach presentations made veteran service events. This form also will be provided to all VHA clinicians from whom we recruit, in mental health clinics, PTSD clinics, and primary care clinics. The 10-5345 form will be presented to interested veterans during their clinical sessions. If the veteran expresses interest and consents to release contact information, the form

will be signed and dated. The clinician will then contact a research project staff member to state that a release has been signed. The 10-5345 form is included in this submission.

In addition to the above described recruitment strategies, we will also post flyers and brochures throughout the VA Boston Healthcare System announcing the research treatment study and providing a contact number for interested veterans to call and obtain additional information about the study.

Recruitment will involve several steps. First, interested veterans will speak with a project staff member who will provide detailed information about the research treatment study. If the veteran continues to express interest, a brief screen will be conducted. If the veteran appears eligible for the study based on the phone screen (see phone script included in this submission), an initial in person assessment will be scheduled. At the first in-person session, the veteran will again be provided with a thorough description of the project as part of the informed consent process. After providing informed consent, the veteran will complete a demographic form and basic health questionnaire, administration of the MoCA and WRAT and discussion of his willingness to adhere to the study conditions. Administration of the CAPS and SCID, as well as completion of the self-report battery will then take place.

**Non-inclusion of Children, Adolescents, and Women in the Study Sample:**

Individuals 18 and older will be eligible to participate in the study, however, we expect very few participants will be under the age of 21 give the available data on age of veterans presenting for PTSD services at VA clinics. This project will not include women for several reasons. First, the number of female veterans is considerably smaller than male veterans. Second, women veterans presenting with PTSD are more likely to have PTSD resulting from sexual trauma, relative to male veterans (approximately 71% among women compared with 4% for men; Fontana et al., 2007). Because of the different nature of trauma causing PTSD and the distinct needs of women veterans, the VA healthcare system has developed women only trauma specialty programs to better serve women veterans (e.g., locations in Boston, Madison, Albuquerque, and Palo Alto VA sites). The VA system has found that women are more likely to present for and participate in treatment if the clinic serves women only. Despite the development of these specialty clinics, 89% of veterans who present to the VA healthcare system for PTSD treatment are men (Desai et al., 2010). We considered running mixed male-female groups but recognized that the nature of the trauma exposure would likely be very different for male and female participants, which would require substantial revision to the GCBT program that is being tested here. In addition, women veterans with PTSD are very unlikely to participate in treatment groups that include male members. Given this, we felt that it was scientifically appropriate to start with single-sex (male) groups, which will require a small degree of treatment modification. Additionally, given that 89% of veterans presenting for PTSD treatment are men, it is very unlikely that we would be able to recruit sufficient number of women to run women only treatment groups. Taken together, for both scientific and clinical practice reasons, women will not be recruited in the proposed clinical trial.

**D. 3. Procedures for conducting RCT: GCBT versus SGP**

**Recruitment and management of participants:** One of the difficulties in conducting a study of any group treatment is that participants who have enrolled in the study must wait until

a sufficient number of participants have collected to form a cohort. We proposed two approaches to manage this difficulty. First, recruitment will occur in “waves,” meaning that there will be 1-month intervals (every 3-4 months) where referrals will actively be sought. During these waves, efforts to screen and assess potential participants will be maximized, to concentrate resources on the formation of a cohort (14 participants). During the recruitment process, each participant will be made aware of the research requirements and have a chance to decline participation. Second, the project coordinator, with assistance from [name], will work with each participant as soon as he is enrolled in the study. The project coordinator will provide interim clinical care and remain in close contact with the participant while he is waiting for treatment to begin. As reported by Schnurr et al. (2001), this approach appeared successful in reducing attrition from the Cooperative 420 study, as only 3.7% of their PTSD veteran participants dropped out prior to randomization. As discussed in Section D.1, we will recruit 280 potential participants, for a final  $n$  of 196 to begin the trial (70% enrollment). Recruitment will occur in 7 waves (Year 01-1 wave, Year 02: 2 waves, Year 03: 2 waves, Year 04: 2 waves; Year 05: 0 waves); each wave will include 14 enrolled Veterans (20 to be screened to reach this target). The project coordinator will maintain close contact with each veteran throughout each step of the study.

**Training therapists/Between-site coordination:** A challenging aspect of a multi-site trial is implementation of procedures to ensure consistency across sites. In particular, consistency with respect to therapist delivery of GCBT and *SGP* is a paramount concern in this trial. In order to ensure that therapists at both sites are trained thoroughly and consistently, a *2-day* training will be scheduled at the start of the project. Because all project therapists will be experienced in treating combat-related PTSD in veterans, emphasis will be placed on mastery of the specific components of GCBT and *SGP*. Discussion will be included concerning expected, acceptable, and prohibited elements, in keeping with the design of this RCT. Additionally, therapists will meet weekly (by phone or in person) with the either [name] (GCBT) or [name] (*SGP*) for on-going supervision and discussion of adherence with the appropriate treatment manual.

**Randomization:** A methodological issue arises concerning randomization, which is intrinsic to studies involving group treatment. One should randomly assign each participant as they enter the study to a given treatment condition. Within a study examining group psychotherapy, randomization implies a brief wait for individual participants, which is necessary in order to collect enough participants who can then be randomized into one of the two group treatments. As noted in Section E.2, we will safeguard our participants during this wait interval preceding treatment through provision of contact and support from the project coordinator. The project coordinator will meet with each participant in order to assess current functioning and assist in problem-solving specific issues of daily-living. Greater details concerning these proposed procedures are found in section E.2. Additionally, from a methodological standpoint, it makes sense to stratify patients based upon pre-treatment CAPS severity score, if considerable variation exists in the sample’s pre-treatment scores. Related research with this population suggests that the variability in CAPS total severity score will be fairly restricted and that eligible participants are likely to show severe levels of PTSD on the CAPS. For example, the pre-treatment CAPS Total scores in Monson et al. (2006) ranged from 76.7 to 79.1 with a SD of 2.6 to 3.5. These data indicate that we are likely to have insufficient variability in the sample for

stratification. However, in the event that considerable variability does occur, patients will be stratified based on their pre-treatment CAPS total score and randomly assigned to condition within strata. The project statistician will be responsible for randomization of participants.

**Therapists: Background and assignment to condition:** In this proposed study, we elected to nest therapists within condition for **three** reasons. **First**, we have no reason to suspect that study therapists will have particular enthusiasm for either treatment, as they have not been involved in the development of this project. **Second**, because these two treatments share some common features (e.g., facilitation of a supportive environment, provision of information about PTSD), we are concerned that therapists might become confused if counterbalanced. **Third**, therapists will be equivalent with respect to skill level, experience with veterans, and other factors that potentially could be confounds (e.g., sex ).

Each treatment group at each site will be conducted by two therapists. Therapists will be doctoral level psychologists, who have a wealth of experience treating veterans with PTSD. The therapists also will have extensive experience delivering CBT and delivering group treatment. Therapists in the two treatment conditions will be matched for experience and demographic characteristics (e.g., race, sex). These procedures will ensure that any observed treatment condition differences are not due to therapist effects.

**Treatment Procedures:** The two treatments to be used in this study will be delivered using structured treatment manuals (as described in Section D.2; see Appendix). Each therapist team will meet with either [name] or [name] once per week for supervision. Each treatment session will be recorded to permit close supervision and assessment of treatment fidelity and integrity. [name] will serve as supervisor for GCBT and [name] will serve as supervisor for *SGP*.

**Treatment fidelity and integrity** will be assessed by two individuals who are otherwise unaffiliated with the project. These two individuals will be selected owing to their familiarity with either GCBT or *SGP* protocol. For each treatment condition, 20% of the treatment sessions will be randomly selected, reviewed and rated, using the adherence and competence form that was developed during R21 MH64777. This form will be modified to be appropriate for both GCBT and *SGP* (the original version of this form is included in the Appendix).

**Care Path after Participation is Complete:** Participants may have residual needs after participation. Because post-treatment and follow-up evaluations will include assessment of PTSD, depression, related anxiety problems, and substance use, we will be able to ascertain remaining treatment needs. If an individual continues to report significant distress or interference from a specific problem, he will be referred to appropriate services within the VA Boston. Where participants are referred will be determined based on their individuals needs. Referrals will always be made after discussion with the veteran.

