C. 2. Preliminary Studies: This investigative team has experience with research focusing on psycho-pathology, assessment, and treatment of PTSD. The work that is particularly germane to this application stems from a development grant from NIMH (R21 MH64777, PI [name]) that provided preliminary support for a GCBT to treat	CAPS Avoid/ Numbing	22.8 (6.7)	11.1 (8.6)	7.2 (7.6)	21.9 (7.5)	20.9 (12.6)	.89
	CAPS Phy. Hyper.	17.4 (6.5)	9.5 (7.9)	7.3 (7.7)	16.9 (5.7)	13.1 (8.0)	.43
	# patients PTSD +	17/17 (100%)	2/17 (11.7%)	1/15 (6.7%)	16/16 (100%)	11/16 (68.7%)	
	IES-R Intrusion	1.8 (0.8)	0.9 (0.9)	0.7 (0.7)	2.2 (0.9)	1.9 (1.2)	1.04
	IES-R Avoidance	1.5 (0.8)	0.7 (0.8)	0.6 (0.8)	1.8 (0.9)	1.5 (1.0)	.83
	IES-R Phy.	1.8 (0.9)	1.3 (1.2)	0.9 (0.8)	2.5 (1.0)	2.3 (1.1)	.83
	Hyper.						

PTSD. The initial part of this grant developed the GCBT protocol, including writing the manual devising instruments to assess therapist adherence and competence, and testing the treatment with several groups of patients ([name] & Coffey, 2005). The second part of this grant included the conduct of a small RCT ([name], Coffey, Foy, Keane, & Blanchard, 2008). Individuals ( $N = 45$ ) with chronic PTSD related to a serious MVA were randomly assigned to either GCBT or a minimum contact comparison group (MCC) in which patients were repeatedly contacted by phone, to assess current functioning and symptomatology.

As reported in **Table 1**, compared with the MCC participants, individuals who received GCBT showed significant reductions in PTSD symptoms, whether assessed using clinical interview (using assessors who were unaware of treatment status & assessment point) or self-report measures. Following treatment, 88.3% of GCBT participants did not satisfy criteria for PTSD, relative to 31.3% of the MCC participants. Examination of anxiety and depression measures did not show a unique advantage of GCBT, although reduced power from the small sample size is relevant here. Treatment-related gains were maintained over a 3-month follow-up interval. Patients reported satisfaction with GCBT and attrition from this treatment was comparable with other individual-format CBT's (see also [name] et al., 2009).

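### The reason given for not stratifying on baseline CAPS is a highly implausible SD, and the fallback stratification rule has no threshold, strata or timing

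*Combined protocol and SAP*

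**What the plan says.** Section D.3 (Randomization) endorses stratifying on pre-treatment CAPS severity "if considerable variation exists in the sample’s pre-treatment scores". It then argues that the condition is unlikely to be met, because earlier work "suggests that the variability in CAPS total severity score will be fairly restricted". The one example is an earlier trial of individual cognitive processing therapy in veterans, whose pre-treatment CAPS totals "ranged from 76.7 to 79.1 with a SD of 2.6 to 3.5". The plan concludes: "These data indicate that we are likely to have insufficient variability in the sample for" stratification.

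A fallback follows: "in the event that considerable variability does occur, patients will be stratified based on their pre-treatment CAPS total score", with random assignment inside strata. No amount of variability, cut-point, number of strata or decision time is given.

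Recruitment runs in waves, and "each wave will include 14 enrolled Veterans (20 to be screened to reach this target". Section D.1 places the CAPS at the in-person intake assessment, and D.3 has men gathered before they are randomized to one of two groups of 7.

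On the analysis side, the Analytic approach text uses t-tests to look for pre-treatment differences and brings those found into the models. Under Hypothesis 1, section D.7.a centres the growth-model intercept on pre-treatment. It offers regression of the slope on the intercept as one example of how to handle any baseline differences.

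**The concern.** The cited SD carries the whole argument against stratifying. If it does not describe spread between patients, the plan has no stated reason for leaving out a step that it calls sensible when scores vary.

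The fallback does not repair this, because it is not yet a rule. Someone must decide what counts as considerable variability, on which men, and when. The plan could be read as judging this on the whole sample, which is unknown when early cohorts are allocated, or on each cohort. Either way, the allocation method could be picked after scores are seen and could differ between waves. The analysis would then have to represent a mixture of schemes that nobody specified in advance.

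**Working it through.** **1. The cited sentence on its own terms.** The range 76.7 to 79.1 spans 2.4 points. Values confined to a range have an SD of at most half that range: 2.4 / 2 = 1.2. With the n − 1 divisor the worst case (n = 2) is 1.2 × √2 = 1.70. Neither reaches 2.6, so 76.7 and 79.1 cannot be the extremes of individual scores and must be group means. Close group means say nothing about spread between patients.

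**2. Comparison with the plan's CAPS pilot data.** The inputs are the pre-treatment columns of Table 1 in section C.2, which covers patients "with chronic PTSD related to a serious MVA were randomly assigned".

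| Subscale | GCBT SD | Comparison SD |
|---|---|---|
| "CAPS Avoid/ Numbing" | 6.7 | 7.5 |
| Hyperarousal | 6.5 | 5.7 |

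Each single subscale SD exceeds the SD cited for the whole scale. For the sum of two subscales, SD = √(s₁² + s₂² + 2·r·s₁·s₂).

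- At r = 0: √(6.7² + 6.5²) = 9.3 (GCBT) and √(7.5² + 5.7²) = 9.4 (comparison).
- At r = 0.5: 11.4 and 11.5.
- Correlation needed for the sum to have SD 3.5, from r = (SD² − s₁² − s₂²) / (2·s₁·s₂): −0.86 and −0.89. For SD 2.6: −0.92 and −0.96.

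Correlations that negative between symptom clusters of one disorder are not credible, although they are algebraically possible. Adding a third subscale with an assumed SD of 5 to 8 gives a total SD of about 10.6 to 12.4 at r = 0 and 14.9 to 17.4 at r = 0.5.

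**3. Comparison with the plan's veteran data.** Table 2 gives pre-treatment PCL-M values of 63.82 (SD 8.39) and 63.58 (SD 10.35). The coefficients of variation are 8.39 / 63.82 = 13% and 10.35 / 63.58 = 16%. The cited CAPS figures give 2.6 / 79.1 = 3% to 3.5 / 76.7 = 5%. This is the right population on a different scale.

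**4. Chance imbalance.** With 98 men per arm, the standard error of the baseline difference is √(2/98) = 0.14 SD units, and its absolute value exceeds 1.96 × 0.143 = 0.28 in 5% of trials. Within a single 7-versus-7 cohort it is √(2/7) = 0.53. In 20,000 simulated trials of 14 cohorts of 14 (normal scores), pairing men by rank within the cohort cut the SD of the overall difference to 0.043 and its 95th percentile to about 0.085.

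**5. What adjustment does.** Let r now be the pre-post correlation, with equal variances and clustering ignored. The variance of an unadjusted change comparison is proportional to 2(1 − r), and of a baseline-adjusted one to 1 − r². The ratio of standard errors is √((1 + r)/2).

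- r = 0.7: √0.85 = 0.92, about 8% lower.
- r = 0.3: √0.65 = 0.81, about 19% lower.

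A chance baseline difference of 0.28 would shift an unadjusted change comparison by (1 − r) × 0.28, which is 0.08 at r = 0.7 and 0.20 at r = 0.3. Once the model adjusts, remaining imbalance costs only about 1 / (196 − 3) = 0.5% in variance. The plan gives no pre-post correlation, so 0.3 to 0.7 is an assumption.

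**The case against.** Three points on the other side have force.

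- **The comparison data are not like for like.** Table 1 comes from accident survivors, while the plan's argument is that treatment-seeking veterans are uniformly severe. The legible rows are subscales, not the CAPS total. The cited trial dates from 2006 and so predates the CAPS-5 used here, so neither SD carries over directly. A reader might infer that the figure cannot be an SD, or that it is certainly a standard error. The documents support neither. They give no sample size for the cited trial. If one assumes the figures are standard errors, the implied SD is 11.6 to 15.7 at 20 per arm and 16.4 to 22.1 at 40, but that remains an assumption. Highly implausible is as far as the documents go, and it is enough, because this is the only figure offered.
- **The fallback could be run in waves.** A reader might infer that it cannot be applied sequentially. But all of a cohort's CAPS scores can be in hand before that cohort is allocated, so a per-cohort rule is feasible. The defect is that the rule is unspecified. A per-cohort trigger would also be imprecise: an observed SD of 12 from 14 men has a 95% interval of about 8.7 to 19.3.
- **Unstratified randomization of 196 men is valid.** A reader might set the 0.28 SD imbalance against the planned effect of 0.50 as if it were bias. It is chance variation, already reflected in the standard error, and the growth model carries a pre-treatment intercept. What remains is that the slope-on-intercept path is tied to observed baseline differences rather than fixed in advance.

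**Conclusion.** The point holds as a modest design weakness. The cited SD of 2.6 to 3.5 is highly implausible as a between-patient SD and conflicts with the plan's own pilot data. By the plan's own criterion, the reason for not stratifying therefore falls away. The fallback lacks a threshold, strata and timing, which leaves room for different waves to be allocated by different schemes.

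The validity of the primary comparison is not threatened. The gain is in balance (SD of the chance baseline difference from 0.14 to about 0.04 with rank pairing) and in precision. Most of the precision comes from unconditional adjustment: a standard error about 8% to 19% lower than an unadjusted change comparison, at assumed pre-post correlations of 0.7 to 0.3. Once adjustment is fixed, stratification adds little precision; its value is balance and a single, reproducible allocation scheme. The planned sample size is unaffected, because the effect is stated in standardized units.

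**What to change.** 1. In D.3, check the cited SD against its source, or delete the argument that rests on it.
2. Replace the conditional trigger with one rule for every wave: each cohort is allocated within strata of baseline CAPS-5 total formed in that cohort. A within-cohort median split or rank pairs would serve. State what happens when a cohort is not exactly 14 or a man leaves between ranking and allocation.
3. In D.7.a, regress the slope on the intercept in every primary model, whatever the pre-treatment t-tests show, and reflect the allocation strata in the analysis.

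The cost is small: a change to the allocation procedure, slightly more preparation per wave, and a few sentences in the analysis section. No new data are needed, since the CAPS is already given before randomization.
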